3.0 ELIGIBILITY

3.1 Inclusion Criteria

- 3.11 Age \geq 18 years.
- 3.12 Histologically or cytologically confirmed malignant secretory or non-secretory pheochromocytoma or paraganglioma that is unresectable and deemed inappropriate for alternative local regional therapeutic approaches.
- 3.13 Measurable disease as defined in [Section 11.0](#).
- 3.14 ECOG Performance Status (PS) 0, 1, or 2 ([Appendix I](#)).
- 3.15 Life expectancy $>$ 24 weeks.
- 3.16 The following laboratory values obtained \leq 14 days prior to registration.
- Absolute neutrophil count (ANC) \geq 1500/mm³
 - White blood cell (WBC) count \geq 3,000/mm³
 - Platelet count \geq 100,000/mm³
 - Hemoglobin \geq 9.0 g/dL (5.6mmol/L)
NOTE: Transfusions are not allowed \leq 7 days prior to registration
 - Total bilirubin \leq 1.5 X upper limit of normal (ULN)
(or total bilirubin \leq 3.0 X ULN with direct bilirubin \leq 1.5 X ULN in patients with well-documented Gilbert's Syndrome)
 - Aspartate transaminase (AST/SGOT) \leq 2.5 X ULN
 - Creatinine \leq 1.5 X ULN
 - Urine protein/creatinine ratio \leq 1 OR 24-hour urine protein $<$ 1.5 gram
- 3.17 Negative pregnancy test done \leq 7 days prior to registration, for women of childbearing potential only.
- 3.18 Blood pressure (BP) $<$ 150 mmHg (systolic) and $<$ 90 mmHg (diastolic). Initiation or adjustment of BP medication is permitted prior to registration provided that the average of three BP readings at a visit prior to registration is $<$ 150/90 mmHg.
- NOTE:** All patients with secretory pheochromocytoma or paraganglioma are REQUIRED to: 1) be evaluated in consultation by a hypertension specialist with specific experience in the management of hypertension in the setting of catecholamine-secreting tumors (usually an endocrinologist, nephrologist, or a cardiologist), and in the setting of hormone-associated hypertension) receive α - and β -adrenergic blockade for at least 7-14 days prior to initiation of lenvatinib (see [Appendix IV](#) for guidelines regarding proper α - and β -blockade). The hypertension specialist of record for each patient should be committed to closely following the patient during the clinical study with evaluation by said specialist required at Cycle 1 and 2 and thereafter on an as needed basis. Please see [Appendix IV](#) for guidelines on hypertension evaluation, follow up and management.
- Please note that this is a critical patient safety issue and that no exceptions to this approach are permitted.**

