Renal and urinary disorders	Proteinuria Grade ≥ 3		Grade 3, hold lenvatinib until it resolves to Grade 2 or less and resume at one reduced dose level (see Section 8.33) Grade 4, discontinue lenvatinib and enter event monitoring
Skin and subcutaneous tissue disorders	Palmoplantar erythrodysesthesia Grade ≥ 2		Grade 2, hold lenvatinib until it resolves to Grade 1 or less and resume at one reduced dose level Grade 3, discontinue lenvatinib and enter event monitoring

CTCAE System/Organ/Class (SOC)	ADVERSE EVENT	AGENT	ACTION**
Skin and subcutaneous tissue disorders	Maculopapular-rash Grade ≥ 2	lenvatinib	Grade 2, hold lenvatinib until it resolves to Grade 1 or less and resume at one reduced dose level Grade 3, discontinue lenvatinib and enter event monitoring
Vascular disorders	Hypertension Grade ≤ 3		Dose adjust and/or hold lenvatinib and continue to manage per Appendix IV ; consultation with expert recommended Grade 4, discontinue lenvatinib and enter event monitoring
Other non-hematologic adverse events (excluding alopecia)	Grade ≥ 3		Grade 3, hold lenvatinib until AE resolves to Grade 1 or less and resume at one reduced dose level Grade 4, discontinue lenvatinib and enter event monitoring

NOTE: If the patient experiences a significant adverse event requiring a dose reduction at the start of the next cycle, then the dose will remain lowered for that entire subsequent cycle. If that cycle is completed with no further adverse events $>$ Grade 2, then the dose may be increased, at the investigator's discretion, one level at a time, in the following cycles.

NOTE: Adverse events requiring a dose-reduction step for any or all drugs beyond the two dose-reduction steps (levels -1 and -2) will be at the discretion of the treating physician, if the decision is made for the patient to be kept on study. These dose reductions must be clearly recorded in reported clinical data.

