Appendix IV Hypertension Management Guidelines

D.1. Guidelines for the management of lenvatinib-Induced Hypertension: Non-secretory tumors

(For secretory tumors please see Section D.2.)

Increases in blood pressure (BP) and cases of hypertension have been associated with many drugs acting on the VEGF pathway. The proposed mechanism for this increase is through inhibition of VEGF-induced peripheral vasodilation. Hypertension following lenvatinib is well documented in clinical trials. With secretory paraganglioma and pheochromocytoma this could be a major toxicity.

NOTE: that hypertension management of secretory tumors is more complex due to the additional risk of hypertension issues in these patients and management is discussed separately below. For example consultation with HTN specialist is required in patients with secretory tumors prior to study initiation.

- While subjects are receiving treatment with lenvatinib, the early initiation of antihypertensive treatment for grade 1 or 2 hypertension to minimize more severe or persistent hypertension is not considered a grade 3 AE.
- Decisions to hold or decrease the lenvatinib dose during treatment must be based on BP readings taken in the clinic by a medical professional.

Recommended Hypertension Monitoring and Management for non-secretory tumors (BP in mmHg)

Grade (CTCAE v4)	Antihypertensive Therapy	Blood Pressure Monitoring	Lenvatinib Dose Modification
Persistent* Grade 1 Pre-hypertension Systolic 120-139 Diastolic 80-90		Standard	No Change
Persistent Grade 2- Moderate Systolic 140-159 Diastolic 90-99 Protocol-specific guidance supersedes any other management guidelines, including CTCAE v4.	Step 1) Initiate anti-hypertensive treatment (calcium channel blocking agents, e.g. amlodipine, are generally the preferred agents) and if needed, after 24-48 hr Rx, increase dose in stepwise fashion every 24-48 hours until BP is controlled or at max dose of Rx Step 2) If BP still not controlled, add another anti-hypertensive Rx, a LA DHP CCB, ACE1, ARB, or ABB; increase dose of this drug as described in Step 1 Step 3) If BP still not controlled, add 3 rd drug from the list of anti-	BP should be monitored as recommended by the treating physician	No change except as described in Step 4

Recommended Hypertension Monitoring and Management for non-secretory tumors (BP in mmHg)

Grade (CTCAE v4)	Antihypertensive Therapy	Blood Pressure Monitoring	Lenvatinib Dose Modification

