	
hypertensives in Step 2; increase dose of this drug as described in Step 1
 
Step 4) If BP still not controlled, discontinue lenvatinib until BP controlled, then resume
 
NOTE: Stopping or reducing the dose of lenvatinib is expected to cause a decrease in BP.
 
The treating physician should monitor the subject for hypotension and adjust the number and dose of anti-hypertensive medication(s) accordingly
		
Persistent Grade 3 Severe Systolic ≥ 160 Diastolic ≥ 100 Protocol-specific guidance supersedes any other management guidelines, including CTCAE v4	
HOLD lenvatinib until systolic BP ≤ 159 and diastolic BP ≤ 99
 
BP management is identical to that for Grade 2 (see Steps 1-4 above) with 2 major exceptions:
 
1) If systolic BP > 180 or diastolic BP > 110 and the subject is symptomatic: optimal management with intensive IV support in ICU; STOP lenvatinib and notify hospital staff that stopping drug may result in a decrease in BP and
 
2) If systolic BP > 180 or diastolic BP > 110 and the subject is asymptomatic, consideration to initiation of 2 new antihypertensives together should be given in step 1 (and dose escalated appropriately as in step 1).
	
BP should be monitored as recommended by the treating physician unless the subject is symptomatic with systolic BP > 180 or diastolic BP > 110 in which case, monitoring should be intensive
	
HOLD lenvatinib until systolic BP ≤ 159 and diastolic BP ≤ 99. After this, lenvatinib may be re-administered. If BP is still Grade 2, manage as described above for Grade 2 hypertension.
 
In most circumstances, if BP cannot be controlled after an optimal trial of antihypertensive medications, consider either 1 dose reduction of lenvatinib when systolic BP ≤ 159 and diastolic BP ≤ 99 or stopping lenvatinib.
 
HOWEVER, If the subject requires hospitalization for management of symptomatic systolic BP > 180 or diastolic BP > 110,

Recommended Hypertension Monitoring and Management for non-secretory tumors (BP in mmHg)

Grade (CTCAE v4)	Antihypertensive Therapy	Blood Pressure Monitoring	Lenvatinib Dose Modification

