All patients with secretory pheochromocytomas or paragangliomas are required to: 1) be evaluated in consultation, and followed by, a hypertension specialization with experience in the management of hypertension in the setting of catecholamine-secreting tumors (usually an endocrinologist, nephrologist, or a cardiologist), and 2) receive α - and β -adrenergic blockade for at least 7-14 days prior to initiation of lenvatinib (see below for guidelines regarding proper α - and β -blockade). The hypertension specialist of record for each patient should be committed to following the patient during the clinical study on an as needed basis.

Recommended Hypertension Monitoring and Management for Patients with Catecholamine-Secreting Tumors (BP in mmHg) (CTCAE SOC Vascular Disorders/Hypertension)

Grade (CTCAE v4)	Antihypertensive Therapy	Blood Pressure Monitoring	Lenvatinib Dose Modification
Persistent* Grade 1 Pre-hypertension Systolic 120-139 Diastolic 80-90	Standard α - and β -adrenergic blockade	Standard	No Change
Persistent*Grade 2- Moderate Systolic 140-159 Diastolic 90-99 Protocol-specific guidance supersedes any other management guidelines.	Step 1) Advance dose of α -adrenergic blocker until BP is controlled or at max dose of Rx. The β -adrenergic blocker dosage should be advanced for a target heart rate of less than 80 bpm. Step 2) If BP still not controlled, add another anti-hypertensive Rx (usually best a calcium channel blocker such as amlodipine), in conjunction with the patient's identified hypertension specialist, increasing dosage of this drug as described in step 1 or as suggested by patient's identified hypertension specialist. Step 3) If BP is still not controlled, consider either 1 dose reduction of lenvatinib or withholding lenvatinib until BP is better controlled. NOTE: Stopping or reducing the dose of lenvatinib is expected to cause a decrease in BP. The treating physician must therefore monitor the subject for hypotension and adjust the number and dose of antihypertensive medication(s) accordingly	BP should be monitored as recommended by the treating physician and patient's identified hypertension specialist	No change except as described in Step 4

Recommended Hypertension Monitoring and Management for Patients with Catecholamine-Secreting Tumors (BP in mmHg)
(CTCAE SOC Vascular Disorders/Hypertension)

Grade (CTCAE v4)	Antihypertensive Therapy	Blood Pressure Monitoring	Lenvatinib Dose Modification

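### The hypertension row of Section 8.2 does not match Appendix IV at Grades 1, 2 and 4, and the secretory-tumor table cites a step it does not contain

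*Combined protocol and SAP*

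**What the plan says.** **Section 8.2.** The vascular-disorders row is labelled "Hypertension Grade ≤ 3". Its action is "Dose adjust and/or hold lenvatinib and continue to manage per" Appendix IV, with expert consultation recommended. The same cell then adds: "Grade 4, discontinue lenvatinib and enter event monitoring".

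**Appendix IV, D.1 (non-secretory tumors).** The dose column gives no change at persistent Grade 1. At persistent Grade 2 it reads "No change except as described in Step 4". Step 4 exists in this table: "If BP still not controlled, discontinue lenvatinib until BP controlled, then resume". The Grade 3 row requires a hold and refers back to all four steps: "BP management is identical to that for Grade 2 (see Steps 1-4 above".

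**Appendix IV, D2 (secretory tumors).** The dose column again gives no change at persistent Grade 1, and the same words as D.1 at persistent Grade 2. The numbered steps stop at Step 3, which says to "consider either 1 dose reduction of lenvatinib or withholding lenvatinib until BP is better controlled". The Grade 3 row requires a hold and refers back to Steps 1 to 3.

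**Both tables.** For dose reductions, persistent means that the grade is met on at least two measurements 7 or more days apart. At Grade 4, both offer permanent discontinuation or, once pressure has come down to 159/99 or below, consideration of a restart one dose level lower after the Principal Investigator has been consulted.

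**The concern.** Section 8.2 and Appendix IV are both operative dose rules for the same event, and at some grades they can lead to different actions. The event matters here. Section 1.3 gives hypertension as the reason for starting at 20 mg rather than 24 mg, and Section 16.41 exempts it from the non-hematologic stopping rule, so patient-level rules carry much of the control. Section 8.0 also asks for strict adherence during the first two cycles. It names Table 8.1, which holds the dose levels that the reductions in 8.2 use; I take the strictness to extend to 8.2.

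If the texts disagree, two investigators can treat the same reading differently and both be following the protocol. Deviations from the hypertension rules then cannot be judged consistently. At Grade 4 the disagreement also decides whether a patient can return to treatment or has moved to event monitoring.

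**Working it through.** No statistical figure is involved, so the check is to set the texts side by side.

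| Grade | Section 8.2, read literally | Appendix IV D.1 (non-secretory) | Appendix IV D2 (secretory) | Result |
|---|---|---|---|---|
| 1 | Adjust and/or hold; manage per Appendix IV | No change | No change | Conflict on a literal reading |
| 2 | Same | No change by default; interrupt at Step 4 if Steps 1–3 fail | No change by default; consider reducing or withholding at Step 3 if Steps 1–2 fail | Different trigger |
| 3 | Same | Hold | Hold | Compatible |
| 4 | Discontinue; event monitoring | Discontinue, or consider a restart | Discontinue, or consider a restart | Conflict |

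**Grade 1.** The 8.2 label includes it and the action carries no qualifier such as *if needed*. Both Appendix IV cells are unconditional.

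**Grade 2.** Appendix IV does not forbid a dose change. It delays one until antihypertensive treatment has been stepped up without success, and it requires persistence. The 8.2 row states neither condition, so the difference is in when lenvatinib may be changed.

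**Grade 3.** A hold satisfies both texts.

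**Grade 4.** The reference to Appendix IV belongs to the sentence on Grades 3 and lower. The Grade 4 sentence in 8.2 has no such reference and no restart option.

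**The inequality sign.** Every other adverse-event row in 8.2 uses ≥ (Grade ≥ 2 or Grade ≥ 3). The hypertension row alone uses ≤, although its own cell goes on to give a Grade 4 action. Both facts suggest a slip. With ≥ the Grade 1 and 2 differences would disappear, but the Grade 4 difference and the step reference would remain.

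**Step count.** D.1 has Steps 1–4, and its Grade 3 row cites four. D2 has Steps 1–3, and its Grade 3 row cites three. The D2 Grade 2 dose cell nevertheless cites Step 4. The only D2 step that changes lenvatinib is Step 3. Borrowing Step 4 from D.1 would give a different rule, namely interruption and resumption with no mention of a reduction.

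**Precedence.** Appendix IV says that protocol-specific guidance overrides other management guidelines. Section 8.2 and Appendix IV are both protocol text, so this does not rank one above the other.

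**The case against.** The best defence is that the 8.2 cell sends the reader to Appendix IV, so it can be read as adjusting or holding in the way Appendix IV directs. Sections 9.5 and 9.72 also refer hypertension management there; 9.72 presents holding lenvatinib as something that may become necessary; and Section 7.2 lets treatment continue when raised pressure is controlled with medication. This has force. For Grades 1 and 2 it makes the problem partly an ambiguity rather than a flat contradiction. It does not remove it, because the sentence joins the two actions with *and* and does not make the first depend on the second. Nor does it help at Grade 4.

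On the D2 reference, it is fair to say that the operative text is present. D.1 is headed for non-secretory tumors and redirects secretory cases to D2, so Step 3 is very probably what was meant. The slip is one of numbering, and the required hypertension specialist reduces the practical risk. The cell still points to nothing in its own table.

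A reader might also infer that a patient entering at, say, 145/85, which Section 3.1 allows ("Initiation or adjustment of BP medication is permitted prior to registration provided that the average of three BP readings" is below 150/90), already meets a Grade 2 dose rule on Day 1. The documents do not support that. Appendix IV requires persistence, and Section 8.0 ties modifications to adverse events since the prior dose, so an unchanged entry pressure is not such an event.

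**Conclusion.** The point stands as an internal inconsistency that should be corrected. It affects one table row at three of four grades: a literal conflict at Grade 1, a different trigger at Grade 2, and a conflict at Grade 4. It also affects one cross-reference in the secretory-tumor table. The Grade 1 and 2 part rests on reading the ≤ sign and the conjunction as printed. The Grade 4 part and the step reference do not depend on that reading.

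Two stronger conclusions are tempting and are not supported. One is that the response rate would depend on which page a site follows. The documents give no figure linking these dose rules to dose intensity or response. The hypertension rates in Section 1.233 (68% overall, 42% at Grade 3 or higher) come from a thyroid-cancer trial at 24 mg and do not show how many patients here would be dosed differently. The other is that the safety note in Section 3.1 marks this dose rule as critical. That note concerns specialist consultation and adrenergic blockade before treatment.

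**What to change.** 1. Reconcile the hypertension row of Section 8.2 with both Appendix IV dose columns so that each grade has one stated action. This includes confirming the direction of the inequality sign, and saying whether adjusting or holding applies only as Appendix IV directs, with its persistence condition and antihypertensive steps.
2. Reconcile the Grade 4 text: Section 8.2 and Appendix IV should agree on whether a restart may be considered.
3. Correct the step reference in the D2 Grade 2 dose cell so that the cell and the numbered steps describe one rule.

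Which action applies at each grade is for the sponsor to decide. The cost is a text amendment to one table row, the matching Appendix IV cells where needed, and one cross-reference. No additional patients, visits or procedures are required.

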8.3 Management of Specific Adverse Events

8.31 Electrolyte abnormalities with or without tumor lysis syndrome

Management of Grade 2 or higher hypokalemia and hyperkalemia, management of Grade 3 or higher hypomagnesemia and hypermagnesemia, Grade 3 or higher hypophosphatemia and Grade 3 or higher hypocalcemia and hypercalcemia.

Management of Abnormal Laboratory Assessments	
Hypokalemia or hyperkalemia \geq Grade 2 Hypocalcemia or hypercalcemia \geq Grade 3 Hypophosphatemia \geq Grade 3 or Hypomagnesemia or hypermagnesemia \geq Grade 3	
 Hold treatment and ECG must be performed Laboratory values should be corrected as soon as possible in a manner consistent with good medical judgment 
 Lenvatinib may be re-administered when 
 hypokalemia or hyperkalemia is Grade 1 or within institutional normal limits hypocalcemia or hypercalcemia is \leqGrade 2 hypophosphatemia is \leqGrade 2 hypomagnesemia or hypermagnesemia is \leqGrade 2

8.32 Management of QTc Prolongation

Table below outlines the management of QTc prolongation of 500 msec and management of QTc prolongation of 60 msec or more from baseline.

Management of QTc Prolongation	
If ECG reveals an increase in the QTc to >500 msec or an increase in the QTc by at least 60 msec from baseline	Hold lenvatinib and repeat ECG ≤ 7 days and before re-administration of lenvatinib
If repeat ECG shows QTc interval is ≥ 500 msec	Discontinue lenvatinib and patient enters the event monitoring
If on repeat ECG, QTc remains at least 60 msec longer than baseline but is <500 msec	Consider discontinuing lenvatinib or increase monitoring after discussion with PI

8.33 Management of Proteinuria

If, at any time, a subject has a urine protein/creatinine ratio greater than 1, a 24 hour urine collection must be performed. If a subject develops the nephrotic syndrome, treatment must be discontinued.

Although subjects with $\geq 1+$ proteinuria at entry are ineligible, increases in proteinuria may occur during treatment and should be managed as follows:

Management of Proteinuria	
UPC >1 and <3	Obtain 24-hr urine protein and if <3.4 g, continue at current dose and monitor as clinically indicated
UPC ≥ 3 or 24-h urine protein ≥ 3.5 g	
Step 1: Hold lenvatinib
 
Step 2: Weekly UPC or 24-hr urine protein monitoring until UPC is <3 or 24-hr urine protein is <3 grams
 
Then restart lenvatinib one dose level less
 
Step 3: If UPC >3 or 24-h urine protein ≥ 3 g recurs, repeat Steps 1 and 2
 
Step 4: If UPC ≥ 3 or 24-hr urine protein ≥ 3 recurs and the lenvatinib dose can no longer be reduced, discontinue lenvatinib and remove subject from study

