4.0 STUDY CALENDAR

4.1 Test Schedule

Tests and procedures ¹				Active Treatment				End of Treatment	
	≤28 days prior to registration	≤14 days prior to registration	≤7 days prior to registration	Cycle 1			Prior to Day 1 of subsequent cycles ³	Every 2 months	
				D1	D3	D10 ²			
Tests and procedures ¹	Window:						±3 days	±7 days	±14 days
Clinical Procedures									
Vital signs, history (including personal/family history for prolonged QTc) and exam, weight, PS		X		X	X	X	X		X
Height		X							
Review of concurrent medications ⁴		X					X		
Pregnancy test ⁵			X						
Blood pressure monitoring ⁶		X		X	X	X	X		
Adverse event assessment		X		X	X	X	X		X
Consultation with endocrinologist, cardiologist, or nephrologist for blood pressure management		X					X		
Hematology: CBC/diff ⁷		X					X		X
Chemistry Panel ⁸		X					X		X
TSH		X					X		
24 hr urine catecholamine and metanephhrines		X					X		
Plasma fractionated metanephhrines		X					X		
Urinalysis ⁹		X					X		
Urine protein/creatinine ratio		X					X		
Genetic counseling and testing at discretion of patient and counselor ¹⁰	X								

¹ All tests and procedures are clinically indicated, unless noted with an R to indicate funding by research

² May be omitted at discretion of treating provider and replaced with telephone call contact.

³ If patient is tolerating treatment well, return visits may be performed over the phone for non-imaging cycles (starting with cycle 3, 5, 7 etc.). During these phone visits the patient status, treatment information, and Adverse Event Assessments must be assessed and recorded. Labs may be done locally and transmitted to Mayo Clinic.

⁴ Concurrent/concomitant medications are reviewed every cycle. Only requested medications are recorded in the study case report forms.

⁵ For women of childbearing potential only. Must be done ≤7 days prior to registration

⁶ Note: 1) daily monitoring of blood pressure is REQUIRED and must be recorded in patient diaries throughout the entire duration of therapy; 2) any systolic BP >150 mm Hg and/or diastolic BP >100 mm Hg must be brought to the attention of treating provider <24h after noted; 3) any systolic BP >200 mm Hg and/or diastolic BP >110 mm HG should prompt immediate cessation of lenvatinib therapy maintained until remediation to <150 mm Hg systolic is accomplished.

⁷ Must include: hemoglobin (hgb), MCV, leukocyte count, neutrophils (ANC), monocyte count, lymphocyte count, and platelet count (PLT)

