9.75 Proteinuria

Urinary protein/creatinine ratio should be frequently monitored to screen for proteinuria as it is a known adverse event associated with antiangiogenic agents including lenvatinib. Specific guidelines for management of proteinuria are presented in [Section 8.2](#) and [Section 8.33](#).

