Persistent* Grade 3 Severe Systolic ≥ 160 Diastolic ≥ 100 Protocol-specific guidance supersedes any other management guidelines.	HOLD lenvatinib until systolic BP ≤ 159 and diastolic BP ≤ 99 BP management is identical to that for Grade 2 (see steps 1-3 above) with 2 major exceptions: 1) If systolic BP >180 or diastolic BP >110 and the subject is symptomatic: optimal management is with intensive IV support in ICU; STOP lenvatinib and notify hospital staff that stopping lenvatinib may result in a decrease in BP and 2) If systolic BP >180 or diastolic BP >110 and the subject is asymptomatic, Consultation with patient's identified hypertension specialist is required as to the proper medical therapy, addition of additional anti-hypertensive medications and monitoring. NOTE: Stopping or reducing the dose of lenvatinib is expected to cause a decrease in BP. The treating physician should monitor the subject for hypotension and adjust the number and dose of antihypertensive medication(s) accordingly	BP should be monitored as recommended by the treating physician and patient's identified hypertension specialist unless the subject is symptomatic with systolic BP >180 or diastolic BP >110 in which case, monitoring should be intensive.	HOLD lenvatinib until systolic BP ≤ 159 and diastolic BP ≤ 99 . After this, lenvatinib may be re-administered. If BP is still grade 2, manage as described above for grade 2 hypertension. In most circumstances, if BP cannot be controlled after an optimal trial of antihypertensive medications, consider either 1 dose reduction of lenvatinib when systolic BP ≤ 159 and diastolic BP ≤ 99 or stopping lenvatinib. HOWEVER, If the subject requires hospitalization for management of symptomatic systolic BP >180 or diastolic BP >110, permanently discontinue lenvatinib or if BP is controlled to systolic BP ≤ 159 and diastolic BP ≤ 99, consider re-starting lenvatinib at 1 lower dose level after consultation with the study Principal Investigator
Grade 4 Life-threatening consequences of hypertension	Optimal management with intensive IV support in ICU; Contact of patient's identified hypertension specialist. STOP lenvatinib and notify hospital staff that stopping lenvatinib may result in a decrease in BP	Intensive	Permanently discontinue lenvatinib or if systolic BP ≤ 159 and diastolic BP ≤ 99 , consider re-starting lenvatinib at 1 lower dose level after consultation with the study Principal Investigator

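### Section 8.33: the proteinuria hold and restart conditions overlap, so a patient held on 24-h protein of 3.5 g or more with UPC below 3 already meets the Step 2 restart condition

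*Combined protocol and SAP*

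**What the plan says.** Section 8.33 has an opening rule and a two-row table.

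- **Opening rule**, applying at any time during treatment: if "a subject has a urine protein/creatinine ratio greater than 1, a 24 hour urine collection must be performed". Nephrotic syndrome requires discontinuation.
- **Row 1**, UPC above 1 and below 3: "Obtain 24-hr urine protein and if <3.4 g, continue at current dose and monitor as clinically indicated".
- **Row 2**, UPC at least 3 or 24-h protein at least 3.5 g: Step 1 holds lenvatinib. Step 2 reads "Weekly UPC or 24-hr urine protein monitoring until UPC is <3 or 24-hr urine protein is <3 grams", followed by restart one dose level lower. Step 3 repeats Steps 1 and 2 if UPC is above 3 or 24-h protein is at least 3 g again. Step 4 discontinues when no further reduction is possible.

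Two other places bear on restart. The proteinuria row of Section 8.2 says "Grade 3, hold lenvatinib until it resolves to Grade 2 or less and resume at one reduced dose level" and refers to 8.33. Section 7.2 lets treatment continue at Grade 3 or lower, or at 24-h protein up to 3.5 g.

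UPC is the routine measure. Section 9.75 says "Urinary protein/creatinine ratio should be frequently monitored to screen for proteinuria", and the Section 4.1 schedule lists "Urine protein/creatinine ratio" but no 24-h urine protein; its only 24-h urine is for catecholamines and metanephrines.

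**The concern.** An either/or trigger needs a release condition that fails for as long as either trigger is still met. Step 2 does not meet that need. The 24-h trigger adds something to the UPC trigger only when UPC is below 3, and those are the patients for whom Step 2 is already satisfied. Row 1 lets a high 24-h value override a UPC below 3; Step 2 lets a UPC below 3 override a high 24-h value.

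The stakes are patient safety and consistent dosing. A site could restart at the first weekly check while 24-h protein is still 3.5 g or more. Restarting too early can also cost dose: Step 3 re-holds at 3 g, so a patient who has not recovered could go from 20 to 14 to 10 mg and then reach Step 4. The Section 8.2 note leaving reductions beyond level -2 to the treating physician softens this. Two sites could also treat the same readings differently.

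**Working it through.** This is a check of logic. The plan gives no figure to reproduce, and no power or sample-size formula applies.

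**Inputs, all from 8.33**

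- Hold = UPC ≥3 or 24-h protein ≥3.5 g (row 2).
- Release as written = UPC <3 or 24-h protein <3 g (Step 2).
- Release as proposed = UPC <3 and 24-h protein <3 g.

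**All combinations of the cut-offs**

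| UPC | 24-h protein | Hold | Release as written | Release as proposed |
|---|---|---|---|---|
| <3 | <3 g | no | yes | yes |
| <3 | 3 to <3.5 g | no | yes | no |
| <3 | ≥3.5 g | **yes** | **yes** | no |
| ≥3 | <3 g | yes | yes | no |
| ≥3 | 3 to <3.5 g | yes | no | no |
| ≥3 | ≥3.5 g | yes | no | no |

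A hold applies in 4 of 6 combinations. As written, hold and release are both true in 2 of those 4; as proposed, in 0 of 4. The row in bold is the error raised here. Example: UPC 2.5 with 24-h protein 4.0 g is a hold (4.0 ≥ 3.5) and also a release (2.5 < 3).

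**Can a patient get there?** Yes, by row 1: UPC between 1 and 3 leads to a 24-h collection, and a result of 3.5 g or more leads to row 2. To see which readings are involved, assume 24-h protein = UPC (g/g) × daily creatinine excretion. This relation and the excretion values are assumptions, not document figures.

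- The overlap needs excretion above 3.5 / 3 = 1.17 g/day.
- At 1.2, 1.3, 1.5 and 1.8 g/day it starts at UPC 3.5/1.2 = 2.92, 3.5/1.3 = 2.69, 3.5/1.5 = 2.33 and 3.5/1.8 = 1.94, and runs up to 3.
- For 24-h protein to be 3.5 g or more with UPC at or below 1, where no collection is compulsory, excretion would have to be at least 3.5 / 1 = 3.5 g/day, about twice the highest assumed value (3.5 / 1.8 = 1.94).

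The overlap is therefore reachable, but under this assumption it lies where 8.33 already requires a 24-h collection.

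**Timing.** With the 28-hour half-life in Section 15.15, the first weekly check comes 7 × 24 / 28 = 6 half-lives after the last dose. The documents do not say how fast proteinuria falls, so some patients will have recovered by then and others may not.

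**Does other text settle it?** Section 8.2 gives no gram cut-off and points back to 8.33. Section 7.2 also joins its two criteria with 'or'. Neither clearly removes the overlap.

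**The case against.** The strongest reply is that Section 8.33, read whole, does not let a high 24-h value go unseen. Any UPC above 1 forces a collection, and a result of 3.5 g or more sends the patient back to row 2. This largely stands. A reader might infer that restart takes place blind to the 24-h value; the documents do not support that. The high value would normally be on file and row 2 would call for a hold again. What is left is a table that says hold and restart for the same patient.

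A second reply is that Step 2 is meant distributively: follow one measure until that measure is below its own limit. The Step 3 trigger of 3 g, the exact complement of the Step 2 limit, suggests this intent. It is a fair reading, but Step 2 also lets the site choose which measure to follow, and UPC is the routine one. The reading therefore does not secure the 24-h value.

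Third, a reader might see a conflict with the Grade 2 condition in Section 8.2. That would require 24-h protein of 3.5 g or more to be Grade 3, and the documents leave grading to CTCAE without giving cut-offs, so no conflict can be shown.

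Fourth, comparison with other hold rules helps only a little. Grade 3 hypertension in Appendix IV ("HOLD lenvatinib until systolic BP" at most 159 and diastolic at most 99) does require both values, but they come from a single measurement. The QTc rule repeats the ECG "and before re-administration of lenvatinib", yet may allow treatment to go on with QTc still 60 msec or more above baseline, so it is not a precedent.

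Finally, Section 8.0 treats the modifications as guidelines after the first two cycles, which leaves room for clinical judgement. In those first two cycles they are to be followed strictly.

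**Conclusion.** Step 2 is wrong as written, at low severity. The overlap follows from the cut-offs alone and needs no distributional assumption; only the illustration of reachable UPC values rests on assumed creatinine excretion. Read literally, the rule permits restart one level lower with 24-h protein still at or above 3.5 g.

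The number of patients affected cannot be derived from the documents and is likely to be small. The compulsory collection, the lower restart dose, the re-hold at 3 g and the nephrotic-syndrome stop all limit harm. The primary endpoint, sample size and two-stage decision rule are unaffected.

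A reader might also call the reverse case (UPC at least 3 with 24-h protein below 3 g) an error. The documents do not show that: a 24-h collection may have been meant to override a high spot ratio.

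**What to change.** Reword Step 2 along these lines: *Check UPC weekly, and add a 24-h urine protein whenever UPC is above 1 or the 24-h value caused the hold. Resume one dose level lower only once UPC is below 3 and the latest 24-h protein is below 3 g.*

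Keep 'or' in Steps 3 and 4, where it correctly widens the trigger. For consistency with row 2 and Step 4, change UPC >3 to ≥3 in Step 3. Sections 7.2 and 8.2 need no change for this purpose.

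Tying release only to the measure that triggered the hold is not enough. A patient held at UPC 3.1 with 24-h protein 3.2 g, who later reads UPC 2.9 with 3.6 g, could then restart above the 24-h hold limit. Requiring both measures closes that route.

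The cost is one short amendment. Some holds will last longer, including in the reverse case, so the sponsor should confirm that no 24-h override was intended there. Section 8.33 sets no maximum hold, so a longer wait does not itself end treatment. Since a collection is already required at UPC above 1, a repeat is extra work only once UPC has fallen to 1 or below: after a hold on the 24-h value, or in the narrow case where a UPC-triggered hold left a last 24-h value of 3 g or more.
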